2.3. Aim

The primary aim of the study is to assess mortality, CV events and the rate of vascular and metabolic comorbidities potentially linked to cortisol excess (hypertension, diabetes, dyslipidemia, obesity) in patients with adrenal incidentalomas and calculate HRs for patient groups stratified by cortisol values following the 1-mg overnight dexamethasone test.

Two types of CV events are differentiated:

- ‘major CV events’: clinically symptomatic myocardial infarction or stroke followed by hospitalization, or CV-related death.
- ‘minor CV events’: any other type of myocardial infarction and therapeutic procedures for coronary heart disease (PTCA, surgical bypass), any stroke, transient ischemic attack, heart failure, deep vein thrombosis, pulmonary embolism.

CV events are optimally registered by hospital medical records reporting one (or more) of the followings: acute myocardial infarction and related therapeutic procedures (PTCA, surgical bypass), stroke, TIA, heart failure, deep vein thrombosis, pulmonary embolism, sudden death, or death from cardiovascular cause.

However, it will be allowed to obtain data with telephonic interview using a structured questionnaire aimed to recognize the presence of the above-mentioned comorbidities and the occurrence of major CV events (clinically symptomatic myocardial infarction, stroke, death).

We will assess:

- Overall Survival (OS) as primary endpoint, defined as the time interval between the date of discovery of adrenal incidentaloma and the date of death from any cause, in patients stratified by different cortisol cut-offs.
- Event-free Survival (ES), defined as the time interval between the date of discovery of adrenal incidentaloma and the date of occurrence of a 'major' and/or 'minor' CV event, in patients stratified by different cortisol cut-offs.
- CV mortality, defined as death from any CV cause, in patients stratified by different cortisol cut-offs. Other causes of death will be specified, as well.

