2.4. Methods

Retrospective, multi-center study

CV events are optimally registered by hospital medical records or can be obtained with telephonic interview using a structured questionnaire aimed to recognize the presence of the above-mentioned comorbidities and the occurrence of CV events.

Statistical analysis:

CV event rates will be expressed as the number of events per 1000 person-years.

Kaplan-Meier analysis will be used to construct survival curves and compute risks. Cox regression will be used for time-to-event analysis, and hazard ratios (HRs) computed with accompanying 95% confidence intervals (95% CI). Analysis will be stratified according to post-dexamethasone cortisol levels with three pre-specified cutoffs: ≤ 50 nmol/L (1.8 μ g/dL), 51-138 nmol/L (1.9-5.0 μ g/dL) and > 138 nmol/L (> 5 μ g/dL). However, additional cutoffs might be analysed as well.

Depending on the level of comprehensive documentation of the patients' characteristics two cohorts will be separately analysed:

- Cohort A: all requested data are available
- Cohort B: patients with missing data, but the following data are available: date of diagnosis the adrenal incidentaloma, result of 1mg DST, and survival status (or date of death).

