2.5. Requested clinical annotations (type, justification)

Inclusion criteria:

- Age ≥ 18 years
- Adrenal mass detected by sensitive imaging tests (CT or MRI) not done for suspected adrenal disease since 1-1-2000 (modified in Oct 2018 to 1-1-1996 to allow longer follow-up time)
- Imaging characteristics typical of adrenal adenoma: unenhanced or delayed enhanced CT, MRI with chemical shift and FDG-PET are all acceptable to secure this diagnosis.

- In the absence of appropriate imaging study, results of 12-month follow-up showing unchanged mass characteristics can be considered as surrogate criterion.
- Availability of 1-mg overnight dexamethasone test results done at diagnosis or during follow-up
- Follow-up duration of at least 36 months (from the date of diagnosing the adrenal mass the first time)
- Availability of follow-up data on living status and occurrence of CV events (telephone interview allowed to capture data)

Exclusion criteria:

- Presence of clinical features of overt Cushing's syndrome
- UFC $\geq 2 \times$ ULN
- ACTH-dependent Cushing syndrome
- Any active malignancy

Minimum clinical annotations:

- Date of birth, date of diagnosis
- Imaging characteristics (mass size, density on unenhanced CT (HU units), absolute or relative wash-out on delayed enhanced CT, results of MRI with chemical shift, results of FDG-PET, or imaging during follow-up > 12 months after initial imaging demonstrating unchanged tumor size)
- Serum cortisol following 1-mg DST, UFC, plasma ACTH (only serum cortisol after dexamethasone will be entered into the statistical model)
- Presence of obesity, hypertension, diabetes, dyslipidemia at initial diagnosis
- Information on prevalent CV events
- Date of last follow-up (date of death)
- Presence of obesity, hypertension, diabetes, dyslipidemia at last follow-up
- Information on incident CV events and date of first event

Minimum expected patient cohort per center: 50

Data acquisition via ENS@T registry

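### A dexamethasone test from any point in follow-up can set the cortisol group, while survival time starts at discovery and no test date is listed

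*Combined protocol and SAP*

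**What the plan says.** Section 2.5 (inclusion criteria) requires "Availability of 1-mg overnight dexamethasone test results done at diagnosis or during follow-up". It gives no window for the test.

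Section 2.3 defines "Overall Survival (OS) as primary endpoint, defined as the time interval between the date of discovery of adrenal incidentaloma" and death from any cause, and "Event-free Survival (ES), defined as the time interval between the date of discovery of adrenal incidentaloma and the date of occurrence" of a CV event. Major CV events are "clinically symptomatic myocardial infarction or stroke followed by hospitalization, or CV-related death", so ES has a fatal part.

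Section 2.4 compares three post-dexamethasone cortisol groups by Kaplan-Meier and Cox methods and adds that "CV event rates will be expressed as the number of events per 1000 person-years". It mentions no delayed entry, landmark or time-dependent exposure.

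The minimum annotations in Section 2.5 list the cortisol result but no date for the test. Cohort B in Section 2.4 needs only "date of diagnosis the adrenal incidentaloma, result of 1mg DST, and survival status (or date of death"). The documents do not say which test counts when a patient has several.

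Section 2.5 also requires "Follow-up duration of at least 36 months (from the date of diagnosing the adrenal mass the first time"). That period runs from diagnosis, not from the test.

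**The concern.** The clock starts at discovery, but the group may be fixed years later. A patient who died before being tested cannot enter the study, so the time from discovery to a late test is guaranteed survival. Counting it as ordinary time at risk lowers the apparent death rate of whichever group the test assigns. This reaches OS, CV mortality and the fatal part of ES.

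Non-fatal CV events raise a different problem. A patient can have one and still be tested later, so the event may be counted against a cortisol level measured after it. The date of the first event is collected, but it cannot be ordered against an undated test.

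At stake are the hazard ratios by cortisol group, which are the study's main product, including those for the primary endpoint.

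**Working it through.** **Inputs.** From the documents: the time origin, the open test window, the three cortisol groups, the missing test date and the 36-month minimum. They state no sample size, event count or target HR, so there is no figure of the plan's own to reproduce. Everything else is assumed: true HR 1.0, 20 deaths per 1000 person-years, 30% of patients in the high group (two groups for simplicity), follow-up uniform over 3–15 years, late tests uniform over a stated window. Inclusion requires being alive and in follow-up at the test. Late shares are before that selection; 40%/10% becomes about 36%/9% among included patients with an 8-year window and the 36-month rule binding everyone.

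**1. Mechanism by hand.** Let F(t) be the share tested by time t, *l* the late share, *m* the window in years and *h* the hazard. Ignoring censoring, the apparent hazard is the true hazard multiplied by

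A(t) = F(t) / [F(t) + (l/m) × (1 − e^(−h(m−t))) / h].

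At t = 3, with m = 8 and h = 0.02:

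- 40% late: F = 0.6 + 0.4 × 3/8 = 0.75; second term = 0.05 × (1 − e^(−0.1))/0.02 = 0.238; A = 0.75/0.988 = 0.759.
- 10% late: F = 0.9 + 0.1 × 3/8 = 0.9375; second term = 0.0125 × (1 − e^(−0.1))/0.02 = 0.0595; A = 0.9375/0.997 = 0.940.

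The apparent HR at month 36 is therefore 0.759/0.940 = 0.81 when the truth is 1.0. It returns to 1 at year 8, when all tests are done. If all tests fall within 3 years, A = 1 in both groups from month 36 onward, so a rule that removes earlier deaths leaves no OS bias from test timing. With equal late shares the two factors cancel at the null.

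**2. OS hazard ratio over the whole follow-up** (simulation, true HR 1.0):

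| Late share, high/low group | Test window | 36-month rule | HR from discovery |
|---|---|---|---|
| 40%/10% | 0–8 years | binds everyone | 0.94 |
| 10%/40% | 0–8 years | binds everyone | about 1.07 |
| 20%/10% | 0–8 years | binds everyone | 0.98 |
| 40%/10% | 0–5 years | binds everyone | 0.98–0.99 |
| 40%/10% | 0–3 years | binds everyone | 1.00 |
| 30%/30% | 0–8 years | binds everyone | 1.00 |
| 40%/10% | 0–8 years | does not bind deaths | about 0.89 |
| 10%/40% | 0–8 years | does not bind deaths | 1.13 |

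Delayed entry at the test returns about 1.00 in these settings.

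**3. Away from the null.** With equal late testing (30%, 0–5 years) a true HR of 2.0 gives 2.00–2.01. An extreme case (80% late over 8 years, 4% deaths per year) gives 2.036. So equal late testing alone does little to the HR.

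**4. Group change.** Suppose 30% in each group are tested late and some late results fall in the other group from the one at discovery. With 10–20% of late results so placed, a true HR of 2.0 becomes 1.93–1.87, and delayed entry leaves it at 1.93–1.87. A separate run with 15% gave 1.87, and 1.89 with delayed entry. This attenuation needs no link between late testing and group.

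**5. Curves and rates** (30% late in both groups, 0–8 years). Deaths per 1000 person-years fall from 13.0 to 12.4 if the rule binds everyone, and from 20.0 to 17.9 if it does not bind deaths. In the second case 10-year survival from discovery reads 0.835 against a true e^(−0.2) = 0.819, and delayed entry gives 0.818. The rates planned in Section 2.4 are for CV events, so they are affected only through CV deaths; an assumed non-fatal rate of 20.0 stays at 20.0.

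**6. ES.** With equal late testing and no link between earlier events and measured cortisol, the ES hazard ratio is 1.00. A link would move it, in a direction set by the link.

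**The case against.** **The effect on the primary endpoint is small.** On the plain text of the 36-month rule, which states no exception for deaths, the OS effect is about 0–2% unless late testing is strongly group-dependent and extends well past month 36. The 0.94 depends on tests five to eight years after discovery. This stands and limits the severity. It does not dispose of the point, because without a test date nobody can show which case applies.

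**The date may exist.** The annotations are headed as a minimum and data come through the ENS@T registry. A reader might infer that the test date is unavailable; the documents do not show that. They show only that the plan neither requests nor uses it.

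**Silence is not a statement.** Section 2.4 does not say that delayed entry will be avoided. True, but it states no alternative to a clock starting at discovery, and Cohort B is defined without the date.

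**ES bias is speculative.** A reader might infer that ES hazard ratios are materially wrong. That requires an earlier CV event to be related to the later cortisol result, and nothing in the documents says so. I therefore give no ES figure as an estimate. What stands is that such events can be attributed to a group measured afterwards.

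**Most of the fall in death rates comes from the 36-month rule.** Also true: of the fall from 20.0 to 12.4, test timing accounts for 13.0 − 12.4 = 0.6.

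**Conclusion.** The gap is real: the group may be measured late, time starts at discovery, and the listed data do not allow the two to be aligned. Hazard ratios are biased mainly if late testing differs by cortisol group or, for ES, if earlier events relate to measured cortisol. It would be wrong to say only then, because a late result in a different group from the one at discovery also pulls hazard ratios toward 1.

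Direction and size are unknown, since the documents give no data on any of these conditions. The OS range of 0.94 to about 1.07 (36-month rule binding everyone) or about 0.89 to 1.13 (rule not binding deaths) applies to the strongly unequal 40%/10% pattern or its reverse over 8 years; shorter windows or milder imbalance bring it close to 1.00. A reader might infer that the planned hazard ratios are invalid, or biased toward a particular cortisol group. The documents support neither. The change should be made because it is cheap and removes a doubt about the primary endpoint that cannot otherwise be settled.

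**What to change.** - Add the date of the dexamethasone test to the minimum annotations and to the Cohort B data, or extract it from the registry if held.
- Define the index test when there are several, for example the first after discovery.
- Use delayed entry at the index test in the Cox and Kaplan-Meier analyses of OS, ES and CV mortality, and start person-years there.
- Treat CV events before the index test as prevalent.
- Add a sensitivity analysis restricted to patients tested within a fixed window of discovery, for example 6 months. It also checks for group change, which delayed entry does not remove.
- Analyse patients without a test date separately.

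**Cost.** One date field, some re-abstraction and a start-time change in the code. In an assumed example with 30% tested late in both groups over 0–8 years, the Cox analysis of OS loses no deaths. About 11.5% of non-fatal ES events precede the test; losing them widens confidence intervals by about 6% (1/√(1 − 0.115) = 1.06). The 6-month window keeps about 75% of patients.

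Whether the 36-month rule applies to patients who died, and the start time that would follow, should be raised separately; delayed entry at the test does not repair that part.

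### Survival is counted from discovery, but inclusion requires 36 months of follow-up from that same date with no exception for death; applied as written, each cortisol group's mortality risk reads too low

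*Combined protocol and SAP*

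**What the plan says.** All references are to the combined protocol and SAP.

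- **Time origin (2.3, Aim).** OS is "defined as the time interval between the date of discovery of adrenal incidentaloma and the date of death from any cause". The second endpoint has the same origin: "Event-free Survival (ES), defined as the time interval between the date of discovery of adrenal incidentaloma". CV mortality is a third outcome: "CV mortality, defined as death from any CV cause, in patients stratified by different cortisol cut-offs".
- **Eligibility (2.5, Inclusion criteria).** "Follow-up duration of at least 36 months (from the date of diagnosing the adrenal mass the first time"). This is a separate criterion with the same origin as OS. Another criterion asks for data on living status and CV events, but it does not waive the 36 months for patients who died.
- **End of follow-up (2.5, Minimum clinical annotations).** One data item covers both endings: "Date of last follow-up (date of death").
- **Analysis (2.4, Methods).** "Kaplan-Meier analysis will be used to construct survival curves and compute risks". Cox regression supplies hazard ratios, and "CV event rates will be expressed as the number of events per 1000 person-years". Neither delayed entry nor a landmark is mentioned, and no result is labelled conditional on surviving 36 months.
- **Cohort B (2.4, Methods).** The data that must be present are "date of diagnosis the adrenal incidentaloma, result of 1mg DST, and survival status (or date of death"). This relaxes data completeness; it does not say that the 36-month rule is lifted.

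**The concern.** The study is retrospective, so centres select patients when outcomes are already known. A patient who dies in month 20 has 20 months of follow-up and, on the words of the criterion, is ineligible. Everyone who is included has therefore survived to month 36 by selection, while the clock still starts at discovery.

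The absolute results suffer: the Kaplan-Meier mortality risk, the CV mortality risk and the CV event rate in each cortisol group. Event-free survival (ES) becomes inconsistent as well, since a non-fatal CV event in year 1 counts and a fatal one does not. Patients left out at selection cannot be restored by later analysis, so the meaning has to be settled before centres submit data.

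**Working it through.** The plan gives no sample size, event count or expected mortality, so there is no figure of its own to reproduce. All rates below are assumptions.

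**1. OS, constant mortality m.** If only patients with T ≥ 3 years enter and time runs from discovery, Kaplan-Meier estimates S(t)/S(3) = exp(−m(t−3)) for t > 3, and 100% before that. The true curve is exp(−mt).

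| Deaths per 1000 person-years | 3-year risk, true / literal | 5-year risk, true / literal | 10-year survival, true / literal |
|---|---|---|---|
| 10 | 3.0% / 0% | 4.9% / 2.0% | exp(−0.10) = 90.5% / exp(−0.07) = 93.2% |
| 20 | 5.8% / 0% | 9.5% / 3.9% | exp(−0.20) = 81.9% / exp(−0.14) = 86.9% |
| 40 | 11.3% / 0% | 18.1% / 7.7% | exp(−0.40) = 67.0% / exp(−0.28) = 75.6% |

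**2. OS, mortality rising with time.** Take a Gompertz hazard matched to a true 10-year survival of 81.9%, so that cumulative hazard H(10) = 0.20. With a doubling time of 8 years, H(3) = 0.0431 and the literal figure is exp(−(0.20 − 0.0431)) = 85.5%. With a doubling time of 6 years, H(3) = 0.0381 and it is 85.1%. The error falls from 5.0 points to 3.2–3.6 points.

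**3. CV mortality.** At 20 per 1000 with 30% of deaths cardiovascular, the 10-year cumulative incidence is 0.3 × (1 − exp(−0.14)) = 3.9% instead of 0.3 × (1 − exp(−0.20)) = 5.4%.

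**4. CV event rate.** In the first three years only non-fatal events can be seen. The proportional shortfall is therefore roughly f × w, where f is the share of events that are fatal and w the share of person-time in those years. With f of 20–45% and w of 26–40%, that is 0.20 × 0.26 = 5% to 0.45 × 0.40 = 18%. Simulation (CV rates of 10–30 per 1000, other mortality 10 per 1000, accrual from 1996 or 2000, loss 0 or 8% a year) gave the same 5–18%; for example, a true 20 read 16.6–18.9.

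**5. OS hazard ratio.** Simulation (3000 patients, 100 runs, reference rate 15 per 1000, censoring uniform over 3–15 years) with early deaths removed gave 1.52, 2.02 and 2.95 for true ratios of 1.5, 2 and 3. Events fell by about 36–38%. If the ratio is 3 before month 36 and 1.5 after it, the estimate moves from 2.05 to 1.52, so it describes the later period only.

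**6. Risk differences.** No direction can be claimed. At 20 per 1000 and hazard ratio 1.5, the literal 10-year difference is exp(−0.14) − exp(−0.21) = 5.9 points. The truth is exp(−0.20) − exp(−0.30) = 7.8 points if the ratio is constant, but exp(−0.20) − exp(−0.27) = 5.5 points if the groups do not differ before month 36.

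**7. What rewording leaves behind.** The dexamethasone test may be done after discovery, and a patient must survive to be tested. Suppose a fraction p is tested uniformly over years 0–5 at 20 per 1000. The mean survival to test is (1 − exp(−0.10))/0.10 = 0.952, and 10-year survival reads 0.819/(1 − p + 0.952p): 83.1% for p = 0.3 and 83.9% for p = 0.5, against 81.9%.

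**The case against.** **Potential follow-up may have been meant.** Section 2.5 explains the move of the imaging start date back to 1996 as a way to gain follow-up, which treats follow-up as calendar time since imaging. Cohort B requires no last-contact date for survivors, so the 36 months cannot always be checked against last contact, whereas it can be checked against a cut-off date. The combined date item is a data field and does not by itself disqualify early deaths. These points stand as evidence that the text is ambiguous. They do not settle its meaning, because nothing says that a patient who died early stays eligible. It should therefore not be asserted that early deaths will be excluded, only that the criterion as worded excludes them.

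**The comparison between cortisol groups survives.** Hazard ratios by cortisol group are part of the primary aim, and step 5 shows that the OS ratio is preserved under proportional hazards with one reading throughout. This stands and limits the severity. It does not rescue the absolute risks and rates, which sections 2.3 and 2.4 also promise.

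**A reader might infer that the cortisol–mortality hazard ratio is biased because centres read the rule differently.** That is possible but speculative. With half the centres on each reading, no stratification by centre, and 40% versus 20% of patients in the higher-cortisol group, a true ratio of 1.0 reads 0.89–0.93 (1.06–1.13 with the mix reversed). With a 35/30 mix it reads 0.98–0.99; with only 10% literal centres and the 40/20 mix, 0.96–0.98. No section indicates any such split or mix.

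**Conclusion.** The point holds as a matter of absolute risk and of an undisclosed condition on the primary endpoint. Followed as written, the plan yields 0% mortality to month 36 and S(t)/S(3 years) afterwards. At assumed constant rates of 10–40 per 1000 person-years, 10-year survival is overstated by 2.7 to 8.6 points. The overstatement is smaller if mortality rises with time. The CV event rate is about 5–18% too low under the assumptions in step 4.

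The documents do not support the stronger inference that the OS hazard ratio between cortisol groups is wrong: under proportional hazards and uniform application it is not, though it then refers to mortality after month 36. Nor would a potential-follow-up reading make the design free of bias. It removes this particular bias but leaves the smaller survival requirement in step 7, and a similar one from using unchanged imaging at 12 months as a surrogate for diagnosis.

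This should be fixed, but it does not defeat the study's comparison.

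**What to change.** 1. **Reword the criterion** as first imaging at least 36 months before the data cut-off (November 2015 or earlier, if the cut-off is the data-acquisition deadline in section 2.8). Keep patients who died before month 36, censor survivors at last contact, and apply this at all centres. Exempting deaths while still demanding 36 months of actual follow-up from survivors is not enough: at 20 per 1000, 10-year survival then reads 80.8–81.5% instead of 81.9%.
2. **Add a last-contact date** for survivors to the Cohort B list, so that they can be censored properly.
3. **If early deaths cannot be retrieved,** use delayed entry at month 36 for OS and CV mortality at all centres, and label both as conditional on 36-month survival. For ES, keep the definition in section 2.3, state that early fatal events are missing, and use delayed entry as a sensitivity analysis only.
4. **Record the date of the dexamethasone test and of the confirming imaging.** Where either follows discovery, start time at risk at the later of these dates, at least as a sensitivity analysis.

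The rewording costs one sentence; the work is in tracing early deaths, some of which may not be found. Delayed entry for OS leaves the hazard ratio and the conditional curve after month 36 numerically unchanged and corrects the time axis and label. For ES it would remove 16–35% of events and 26–40% of person-time under the assumed rates. Only the date of the first CV event is requested, so patients with an early event could not re-enter with a later one. That is why delayed entry should not be the default for ES.

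### Exclusions cover cortisol excess and active malignancy only, so patients found to have aldosterone excess after incidental detection can enter any cortisol band and may distort the cortisol HRs

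*Combined protocol and SAP*

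**What the plan says.** The eligibility rules are in section 2.5. The hormonal exclusions are "Presence of clinical features of overt Cushing's syndrome", urinary free cortisol at or above twice the upper limit of normal, and "ACTH-dependent Cushing syndrome". The remaining exclusion is "Any active malignancy". Primary aldosteronism and phaeochromocytoma are named nowhere in the document.

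Two inclusion criteria bear on the point:

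- The mass must meet this description: "Adrenal mass detected by sensitive imaging tests (CT or MRI) not done for suspected adrenal disease".
- It must show "Imaging characteristics typical of adrenal adenoma". Where suitable imaging is lacking, a mass that is unchanged over 12 months is accepted instead.

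The hormone data requested are post-dexamethasone cortisol, urinary free cortisol and plasma ACTH, with the note that "only serum cortisol after dexamethasone will be entered into the statistical model".

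Section 2.4 says: "Analysis will be stratified according to post-dexamethasone cortisol levels". The bands are ≤ 50, 51-138 and > 138 nmol/L. Cox regression supplies the HRs, and no covariates are named. Section 2.3 makes OS the primary endpoint. ES and cardiovascular mortality are also assessed, and hypertension is listed among the comorbidities that may be linked to cortisol excess.

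**The concern.** The study relates death, cardiovascular events and comorbidities to one exposure, the post-dexamethasone cortisol value. Aldosterone excess can act on the same outcomes (hypertension, stroke, heart failure) without cortisol being involved. An aldosterone-producing adenoma is an adenoma, so the imaging criterion does not remove it.

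A patient with aldosterone excess and cortisol ≤ 50 nmol/L enters the lowest band and raises its event rate. A patient whose tumour secretes both hormones enters a higher band, where the added risk is counted as part of the cortisol gradient. The first pulls an HR of a higher band against the lowest band down, and the second pushes it up.

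The protocol asks for no result that would identify either patient. The data it requests therefore do not allow these patients to be removed, adjusted for, or examined in a sensitivity analysis.

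**Working it through.** The documents give no sample size, event count or prevalence of other hormone excess, so there is no planned figure to reproduce. The check has two parts.

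**1. Do the criteria close the gap?**

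- *Exclusions.* Three of the four concern cortisol and one concerns malignancy. None removes aldosterone or catecholamine excess.
- *Incidental detection.* This criterion governs why the scan was done. It removes patients imaged because adrenal hormone excess was suspected. It does not remove excess first recognised in the work-up that follows an incidental finding.
- *Adenoma imaging.* This does not remove an aldosterone-producing adenoma. It should remove many catecholamine-secreting masses, but the 12-month stability surrogate can replace it.
- *Requested hormones.* There are three tests, all of the cortisol axis.

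The gap is therefore open for aldosterone excess found after incidental detection. It is narrower for catecholamine excess.

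**2. How far could an HR move?** This is an illustration only, and every input below is an assumption. Let p0 be the share with other hormone excess in the ≤ 50 nmol/L band, p1 the share in a higher band, and r the hazard ratio of that excess. Take the true cortisol HR as 1.5. If hazards multiply and events are rare:

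HR observed = 1.5 × [1 + p1(r − 1)] / [1 + p0(r − 1)]

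| p0 | p1 | r | Calculation | HR observed |
|---|---|---|---|---|
| 10% | 10% | 3 | 1.5 × 1.20/1.20 | 1.50 |
| 1% | 0 | 1.5 | 1.5/1.005 | 1.49 |
| 5% | 0 | 2 | 1.5/1.05 | 1.43 |
| 10% | 0 | 3 | 1.5/1.20 | 1.25 |
| 0 | 5% | 1.5 | 1.5 × 1.025 | 1.54 |
| 0 | 10% | 3 | 1.5 × 1.20 | 1.80 |
| 10% | 5% | 2 | 1.5 × 1.05/1.10 | 1.43 |
| 5% | 10% | 2 | 1.5 × 1.10/1.05 | 1.57 |

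The bias factor runs from 1/1.20 = 0.83 to 1.20. With equal shares it is exactly 1, whatever the value of r.

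That neutrality depends on the hazards multiplying. Suppose instead that an affected patient has hazard r in the lowest band and the larger of r and 1.5 in the higher band. Equal shares then no longer cancel:

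- p0 = p1 = 2%, r = 1.5: 1.5 / (0.98 + 0.03) = 1.49.
- p0 = p1 = 10%, r = 3: (0.90 × 1.5 + 0.10 × 3) / (0.90 + 0.30) = 1.65/1.20 = 1.38.

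The sign of the distortion thus depends on how the other hormone excess is spread over the bands and on how the hazards combine. The requested data do not show the first of these.

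**The case against.** The strongest reply is that the plan is better protected than the exclusion list suggests. The incidental-detection criterion already removes patients who were imaged because hormone excess was suspected, and typical adenoma imaging should remove many catecholamine-secreting masses. Both points stand and narrow the concern. Neither reaches aldosterone excess discovered after an incidental finding.

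A second reply is that the size is conjecture. This also stands. Two of the three lowest-band-only results in the table (1.49 and 1.43) are small shifts. The 1.25 and 1.80 extremes need a 10% share in one band only and a threefold hazard. Nothing in the documents supports that hazard, least of all for all-cause death.

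A reader might infer four stronger things that the documents do not support:

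- *That the HRs are known to be biased, or biased toward 1.* The direction is not known, and the bias can be nil.
- *That the lowest band is a declared non-functioning comparator.* Section 2.4 defines the band but names no reference group.
- *That affected patients could never be identified.* Section 2.5 sets minimum annotations and takes data through a registry whose other fields are not described. What is shown is that this protocol does not request the information.
- *That the note on entering only post-dexamethasone cortisol bars all covariates.* It sits with the three hormone tests and may simply choose among them.

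A further objection concerns remedies. Excluding cases documented during follow-up would select on post-baseline information, which depends on length of follow-up and intensity of work-up. Restricting to patients without hypertension would condition on a possible effect of cortisol. Both objections are sound, and the fix below keeps both out of the main analysis.

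**Conclusion.** The concern holds as an eligibility and data gap. As section 2.5 is written, a patient with an incidentally found adenoma and aldosterone excess recognised afterwards may enter any cortisol band. A catecholamine-secreting mass may do so less often, mainly through the stability surrogate. Such patients can distort the cortisol HRs for OS, ES and hypertension.

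The size cannot be derived from the documents. For a true HR of 1.5, shares of 0 to 10% per band and r between 1.5 and 3, the multiplicative model gives 1.25 to 1.80. It gives no distortion when shares are equal. The omission is certain from the text, whereas material distortion is only possible. This does not invalidate the study, but it should be corrected because the exposure of interest is cortisol alone and the correction is cheap.

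**What to change.** 1. Add to the exclusions in section 2.5: primary aldosteronism, phaeochromocytoma or other non-cortisol hormone-secreting adrenal tumour documented at the initial work-up.
2. Add one annotation, filled from existing records, for aldosterone and catecholamine screening: excluded, present or not tested. State that 'not tested' counts as available data, so that the field does not move patients out of Cohort A.
3. Repeat the OS and ES HRs as sensitivity analyses: (i) in patients with documented negative baseline screening; (ii) without cases first documented during follow-up.
4. In the main analysis, do not exclude on follow-up information. Do not restrict on absence of hypertension.

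The cost is one exclusion line, one registry field and two repeat analyses, with no new testing. A small number of patients is lost. The field may be missing in Cohort B, which needs only the diagnosis date, the dexamethasone test result and survival status, so analysis (i) may be limited there.
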